1. BACKGROUND

Alcohol (ALC) use disorder (AUD) is an unrelenting public health concern. Approximately 17 million Americans meet criteria for AUD, with 85,000 deaths directly attributable to ALC each year, resulting in an annual economic burden of about \$250 billion. Several medications have been approved for treating AUD (i.e., disulfiram, naltrexone, acamprosate), but these pharmacotherapies are not widely used, nor are they universally effective or appropriate to use in all AUD patients due to contraindications. To address the continued need to improve AUD treatment, identifying novel AUD pharmacotherapies is an NIAAA priority.

A wealth of data indicates that ALC use produces profound changes in the brain glutamate system. Preclinical studies show that chronic or binge-like ALC administration decreases extracellular glutamate levels, which are then increased during ALC withdrawal. These elevated glutamate levels observed during ALC withdrawal can be reduced with further ALC administration, driving a cycle of heavy ALC use and withdrawal periods that characterize AUD. The changes in glutamate homeostasis that occur during the cycle of chronic ALC intoxication and withdrawal have been attributed to altered glutamate transport (e.g., changes in cystine-glutamate exchanger [xCT] and glial glutamate transporter [GLT-1] expression and function). Normalization of extracellular glutamate levels through administration of compounds like ceftriaxone or n-acetylcysteine (NAC), which increase expression of the xCT and GLT-1, attenuates maladaptive brain changes produced by ALC, as well as ALC self-administration and behavioral sensitization in preclinical models.

These preclinical data provide a strong scientific premise for the hypothesis that normalization of extracellular glutamate levels (i.e., restoration of glutamate homeostasis) is a promising pharmacotherapeutic approach for AUD, yet this research area remains unexamined in prospective clinical studies. Because ceftriaxone must be administered intravenously and can result in serious side effects (e.g., *C. Difficile* infection), as well as antibiotic resistance, it is not feasible for testing as an AUD treatment in clinical research. NAC can be administered orally and has a low incidence of side effects making it an ideal lead compound to be evaluated as a potential medication for treating AUD. Although we are not aware of any clinical studies that have prospectively tested NAC for AUD, there is clinical evidence, including data from our laboratory, supporting its utility in treating other substance use disorders linked to disrupted glutamate homeostasis.

The overarching goal of this application is to demonstrate that restoration of glutamate homeostasis with NAC is a viable strategy for treating AUD. This goal will be achieved through the conduct of a rigorous human laboratory study designed to accomplish three specific aims.

The first aim is to demonstrate that maintenance on NAC reduces the pharmacodynamic effects of ALC that contribute to its abuse. A within-subjects study will be conducted in which non-treatment-seeking subjects with AUD (N=25) will be maintained on placebo and two doses of NAC (1.2 and 2.4 g/day). Two active doses will be tested in order to identify which dose is most effective and should be advanced to a clinical trial. Order of maintenance conditions will be randomly determined for each subject. After being maintained on each dose condition for 4 days, the reinforcing and subjective effects of ALC, including ALC craving, will be determined. Self-reported ALC use in the natural environment during maintenance will also be assessed. This reverse-engineered human laboratory approach has good predictive validity for clinical pharmacotherapy efficacy. After completing a session, subjects will undergo a 1-week washout and begin maintenance on the next condition, repeating this cycle until all conditions have been completed.

The second aim is to demonstrate the safety and tolerability of NAC when combined with ALC. Physiological responses (e.g., heart rate) and breath alcohol levels will be measured throughout each experimental session. Adverse events will also be assessed across each maintenance period in order to demonstrate that NAC can safely be administered to subjects with AUD.

A third, exploratory, aim is to evaluate potential mechanisms contributing to the influence of NAC on the pharmacodynamic effects of ALC. To this end, a number of validated trait measures (e.g., the Zuckerman-Kuhlman Personality Questionnaire, the Barratt Impulsivity Scale) and cognitive-behavioral tasks (e.g., Go/Stop Task, Alcohol Delay Discounting Task) will be completed. Outcomes from these measures will be correlated with pharmacodynamic and safety/tolerability outcomes.

The research proposed here will directly translate findings from preclinical research and provide the initial prospective clinical evidence that restoration of glutamate homeostasis with NAC has promise for treating AUD. This study will also provide basic science information about the glutamatergic mechanisms

Behavioral Effects of Drugs: Inpatient (34) (Alcohol and N-Acetylcysteine) (PI: [name].)
underlying the pharmacodynamic effects of ALC in humans. Overall, the proposed research seeks to expand the scope of current AUD treatment research by focusing on glutamate homeostasis, which has strong preclinical evidence supporting its critical role in AUD but remains unstudied in clinical research.

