2. OBJECTIVES

A within-subject, double-blind, NAC placebo-controlled human laboratory experiment will be conducted to demonstrate that maintenance on NAC attenuates the pharmacodynamic effects of ALC that contribute to its use (Drobes et al., 2003; Hendershot et al., 2016; O'Malley et al., 2002). ALC use in the natural environment, as well as the safety and tolerability of combining NAC with ALC, will also be evaluated.

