4. STUDY POPULATION

Up to 150 individuals will be screened to participate in this study. We intend to enroll 25 (17 male and 8 female) completers into the study. Screening procedures will be conducted under our lab's screening protocol (03-0509). Inclusion and exclusion criteria are outlined below.

Inclusion/Exclusion Criteria

The following criteria must be met for an individual to participate in the study: 1) able to speak/read English; 2) not seeking treatment at the time of the study; 3) female or male between the ages of 21 and 55 years; 4) one binge drinking episode (5+/4+ standard alcoholic drinks per drinking session for men and women, respectively) in the past 30 days; 5) recent ALC use verified by ethyl glucuronide positive urine, as well as fulfillment of DSM-5 diagnostic criteria for AUD; 6) other than the diagnosis for AUD at the time of the interview, subjects must be otherwise healthy; 7) ECG, read by cardiologist, within normal limits; 8) body mass index of 19-35; 9) females using an effective form of birth control and not pregnant or breast feeding; 10) judged by the medical staff to be psychiatrically and physically healthy; 11) able to abstain from ALC for 12 hours prior to session; and 12) no contraindications/allergies to NAC or ALC. Potential research subjects who are seeking treatment for substance abuse/dependence will be excluded from research participation, and will be referred to an appropriate treatment program.

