Subjects will be instructed to maintain their standard diet, ALC and cigarette intake throughout participation, with the exception that they will be asked to abstain from ALC for at least 12h prior to a session. All subjects will provide urine and expired-breath samples prior to experimental sessions. The presence of drugs of abuse in the urine or positive BALs upon arrival for experimental sessions will result in rescheduling of the session. Repeated occurrences will result in study dismissal. Subjects will not be allowed to smoke tobacco cigarettes during experimental sessions, consistent with previous work (O’Malley et al., 2002).

NAC Maintenance Conditions. After completing screening, a subject will be randomized to a NAC dose order condition using a random number generator. Completing subjects will experience all dose conditions. A pharmacist in the Investigational Drug Service will maintain the randomization key to preserve the double blind. NAC doses will be prepared with commercially available drug placed into opaque capsules. Cornstarch will be used as filler. Placebo capsules will contain only cornstarch, but will be visually identical to capsules that contain NAC. Placebo capsules will also be washed in a NAC slurry to control for the

Behavioral Effects of Drugs: Inpatient (34) (Alcohol and N-Acetylcysteine) (PI: [name].)

distinct smell of NAC as has been done in previous research ([name]., Personal Communication). Subjects will receive practice taking the study capsules during the practice session. Subjects will be provided two placebo capsules during this session and instructed on how to correctly administer those capsules. Subjects will be told that these capsules are placebos, but that placebo and NAC capsules will look visually identical.

Total daily doses are 0, 1.2 and 2.4 g/day (i.e., 0, 0.6g and 1.2 g administered two times daily at 0700 and 1900h; Table 1). One of the doses reduced ALC use in one study (i.e., 1.2 g/day; Squeglia et al., 2016) and the other dose reduced elevated brain glutamate levels in another (i.e., 2.4 g/day; Schmaal et al., 2012). Testing two doses in this study will inform dose selection when NAC is advanced to a clinical trial. The dosing regimen and maintenance period were chosen based on previous studies (Amen et al., 2011; LaRowe et al., 2013; Squeglia et al., 2016).

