Data will be analyzed as raw scores. Statistical significance refers to $p < .05$. Number of Drinks Chosen on the ALC self-administration procedure will be analyzed with a one-factor, repeated-measure ANOVA with NAC dose (0, 1.2 and 2.4 g/day) as the factor. A significant attenuation (i.e., decreased ALC self-administration) will be inferred if the main effect of NAC attains statistical significance in the ANOVA. Tukey’s HSD *post-hoc* test will be used to make appropriate pair-wise comparisons between means if the ANOVA outcome attains statistical significance. Data from the subjective-effects questionnaires and safety/tolerability measures following administration of the sampling dose will be calculated as peak effect (i.e., the maximum score observed after ALC sampling). These data will be analyzed in the same fashion as ALC self-administration data. The influence of relevant biological (e.g., age) and behavioral variables (e.g., cigarette smoking, weekly ALC use) will be determined in initial correlation analyses and included as covariates in analyses should they be significantly associated with outcomes. Outcomes from trait questionnaires and cognitive behavioral tasks will also be correlated with self-administration, subjective effect and physiological data to explore the mechanisms by which NAC attenuates the effects of ALC.

Power and Sample Size Considerations. We used the results of a prior meta-analysis of human laboratory studies of ALC self-administration and craving to determine an appropriate sample size for the present experiment (Hendershot et al., 2016). That meta-analysis demonstrated that naltrexone maintenance decreased the quantity of ALC consumed and self-reported craving relative to placebo with an average estimated effect size (i.e., Cohen’s f) of approximately 0.27. Considering the overall design and use of three NAC doses, enrolling 25 subjects will provide sufficient power (power = 0.80, $\alpha = 0.05$, G*Power) to detect a medium effect size (f) of approximately 0.26 for attenuation of the effects of ALC as a function of NAC dose.

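### Aim 2 is worded as a demonstration of safety, but the only stated analysis is a difference test, adverse events have no stated analysis, and nothing says how a non-significant result will be read

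*Combined protocol and SAP*

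**What the plan says.** Section 1 (Background) puts the second aim as a demonstration, twice: "The second aim is to demonstrate the safety and tolerability of NAC when combined with ALC", and then, of adverse events across the maintenance periods, "in order to demonstrate that NAC can safely be administered to subjects with AUD". Section 2 (Objectives) is softer: ALC use in the natural environment, "as well as the safety and tolerability of combining NAC with ALC, will also be evaluated".

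Section 7, Data Analysis, takes the peak of the safety and tolerability measures after the sampling drink and adds: "These data will be analyzed in the same fashion as ALC self-administration data". That means a one-factor repeated-measures ANOVA on NAC dose (0, 1.2, 2.4 g/day), followed by Tukey's HSD if the ANOVA is significant. The threshold is "Statistical significance refers to $p < .05". The only inference rule is that a significant main effect on drinks chosen will be taken as attenuation.

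On size, section 4 says "We intend to enroll 25 (17 male and 8 female) completers into the study", and each completer takes all three conditions. The power statement covers attenuation of ALC effects only. Adverse events are to be collected, reviewed weekly and followed to resolution (section 17), but no section says how they will be summarised or compared. The UKU side-effects scale is completed at the end of each session.

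**The concern.** The aim and the analysis do not match. An ANOVA asks whether the condition means differ. If they do, it gives a signal; if it is not significant, the data may still be compatible with a shift worth knowing about. Only an estimate with its interval, or a test against a stated margin, says how large an effect has been ruled out, and the plan provides neither.

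The gap is wider for the other parts of the aim. The second sentence of the aim rests on adverse events, for which there is no analysis. The UKU, scored once at session end, does not fit a rule that takes the maximum after the sampling drink.

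At stake is what the report may conclude about combining NAC with alcohol. Section 9 itself allows that alcohol's side effects may be more frequent and larger with NAC, so it matters how much the data can exclude.

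**Working it through.** **Inputs.** From the documents: n = 25 completers, m = 3 within-subject conditions, alpha = 0.05, and power 0.80 at f of about 0.26 (for attenuation). Not given, so assumed: correlation between conditions 0.5 and sphericity. The documents give no SDs for the safety measures and no event rates, so shifts are in units of the SD of the paired NAC-minus-placebo difference.

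**1. The plan's own figure.** Noncentral F with lambda = n·m·f²/(1 − rho) = 25 × 3 × 0.26²/0.5 = 10.14, on 2 and 48 degrees of freedom, gives power 0.795 against the stated 0.80. It reproduces. It depends on the correlation: 0.64 at rho = 0.3 and 0.955 at rho = 0.7.

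**2. Chance that a real shift is non-significant.** Paired t, one dose against placebo, two-sided 0.05, no Tukey adjustment, noncentrality = shift × √25:

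| Shift (SD of difference) | Noncentrality | Power | Non-significant |
|---|---|---|---|
| 0.3 | 1.5 | 0.30 | 0.70 |
| 0.4 | 2.0 | 0.48 | 0.52 |
| 0.5 | 2.5 | 0.67 | 0.33 |
| 0.6 | 3.0 | 0.82 | 0.18 |

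The omnibus ANOVA, which is the test actually planned, depends on the dose pattern. At 0.3 and 0.4 SD (rho = 0.5) its power is 0.30 and 0.50 if one dose shifts or both shift equally. It is 0.24 and 0.39 if that shift is reached at the higher dose and halved at the lower.

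**3. What an interval would give.** Half-width of the 95% CI = t(0.975, 24)/√25 = 2.064/5 = 0.413 SD of the difference. If that SD were 10 bpm for heart rate (assumed), this is ±4.1 bpm; if 15 bpm, ±6.2 bpm.

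**4. Events (a separate question from the ANOVA).** With zero events of a given type in 25:
- one-sided 95% upper bound: 1 − 0.05^(1/25) = 11.3%;
- two-sided: 1 − 0.025^(1/25) = 13.7%;
- chance of seeing none when the true rate is 5%: 0.95^25 = 0.277.

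An upper bound below 5% with no events needs 59 subjects, since log(0.05)/log(0.95) = 58.4.

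**The case against.** The strongest reply is that the plan does not commit the error. A reader might infer that a non-significant ANOVA will be reported as proof of safety, or that Aim 2 is met only if nothing is significant. No section says either. The sole inference rule concerns a significant effect on drinking, the Objectives say only that safety will be evaluated, and a significant fall in peak heart rate would hardly defeat the aim. That stands. What remains is that the plan leaves the reading of a non-significant result open while the Background announces a demonstration.

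A reader might also infer that the Aim 2 conclusion decides whether NAC goes forward to a clinical trial. The documents do not support that either: they tie advancement to which dose is most effective and make no safety result a condition.

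It is fair, too, that safety is not left to the ANOVA alone. Section 17 has adverse events assessed daily and at follow-up visits, and section 7 sets cardiovascular limits. These protect individual subjects; they are not an analysis and do not define success for the aim.

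Finally, the study is not blind to larger effects: power is 0.82 at 0.6 SD, and nothing in the documents shows that a shift of 0.3 or 0.4 SD would be clinically important. The event bound uses 25 completers, so counting dosed subjects who drop out would tighten it somewhat. Both points stand and limit the size of the concern.

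**Conclusion.** The concern holds in this form: the stated analysis can flag a difference but cannot support the demonstration of safety that the Background announces, and the adverse events on which half the aim rests have no stated analysis. With 25 completers, shifts of 0.3 to 0.4 SD of the paired difference go undetected about 50 to 70% of the time in a paired t test. An absence of events of one type excludes only rates above about 11% (one-sided) or 14% (two-sided).

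The paired t and event figures rest on n = 25 and standard distributional assumptions. The omnibus figures also rest on an assumed correlation of 0.5, sphericity and the dose pattern shown. The bpm values are illustrations.

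Severity is minor to moderate. The sample size was set for attenuation, reproduces, and is not in dispute; the primary analysis is untouched.

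**What to change.** In section 7, Data Analysis:

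- For each NAC dose, report the NAC-minus-placebo mean difference with a 95% confidence interval for heart rate, systolic and diastolic pressure, BAL and UKU. Use the end-of-session UKU score, because the peak rule does not fit it.
- By condition, among all subjects dosed in that condition, report the number with each adverse event, with exact 95% intervals.
- In the same way and descriptively, report the number crossing each of the two existing sets of cardiovascular limits in section 7 (the set for withholding ALC and the set for exclusion). Show the sets separately and leave the limits unchanged. Give the denominators, since a subject who is excluded contributes no later conditions.
- State that a non-significant ANOVA will not by itself be taken as evidence of safety.

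In section 1, align the two statements that safety will be demonstrated with the verb used in section 2. No clinical margin is needed for this, because it bounds the claim and does not test one.

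The cost is a few sentences, a little extra output from data already being collected, and a more modest safety claim. No subjects, visits or measures are added.

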2. OBJECTIVES

A within-subject, double-blind, NAC placebo-controlled human laboratory experiment will be conducted to demonstrate that maintenance on NAC attenuates the pharmacodynamic effects of ALC that contribute to its use (Drobes et al., 2003; Hendershot et al., 2016; O'Malley et al., 2002). ALC use in the natural environment, as well as the safety and tolerability of combining NAC with ALC, will also be evaluated.

3. STUDY DESIGN

This study will use a rigorous within-subject, double-blind, NAC placebo-controlled human laboratory design with subjects receiving all NAC doses in a randomized order (i.e., NAC is a within subject factor).

4. STUDY POPULATION

Up to 150 individuals will be screened to participate in this study. We intend to enroll 25 (17 male and 8 female) completers into the study. Screening procedures will be conducted under our lab's screening protocol (03-0509). Inclusion and exclusion criteria are outlined below.

Inclusion/Exclusion Criteria

The following criteria must be met for an individual to participate in the study: 1) able to speak/read English; 2) not seeking treatment at the time of the study; 3) female or male between the ages of 21 and 55 years; 4) one binge drinking episode (5+/4+ standard alcoholic drinks per drinking session for men and women, respectively) in the past 30 days; 5) recent ALC use verified by ethyl glucuronide positive urine, as well as fulfillment of DSM-5 diagnostic criteria for AUD; 6) other than the diagnosis for AUD at the time of the interview, subjects must be otherwise healthy; 7) ECG, read by cardiologist, within normal limits; 8) body mass index of 19-35; 9) females using an effective form of birth control and not pregnant or breast feeding; 10) judged by the medical staff to be psychiatrically and physically healthy; 11) able to abstain from ALC for 12 hours prior to session; and 12) no contraindications/allergies to NAC or ALC. Potential research subjects who are seeking treatment for substance abuse/dependence will be excluded from research participation, and will be referred to an appropriate treatment program.

Other than the diagnoses for AUD at the time of the interview, subjects must be healthy. Screening procedures for all subjects will include a medical-history questionnaire, drug-use questionnaire, physical examination, laboratory chemistries (e.g., blood chemistry screen including liver and kidney function tests, hemogram with differential, urinalysis), electrocardiogram (ECG) and a mini-mental status examination. All subjects must have a Body Mass Index (BMI) of 19-35. [name] must consider blood-chemistry, complete blood count and urinalysis values that are not within the normal range clinically insignificant. [name], a cardiologist, or an authorized colleague, will review the results of the ECG. The ECG must be considered to be within normal limits in the opinion of [name] for a potential subject to be enrolled. Any potential subject with a history of serious physical disease, current physical disease (e.g., impaired cardiovascular functioning, histories of seizure, head trauma, or CNS tumors) or current or past histories of psychiatric disorder, other than AUD or tobacco use disorder, will be excluded from research participation. Female subjects must be using an effective form of birth control (e.g., birth control pills, surgical sterilization, IUD, cervical cap with a spermicide or abstinence) in order to participate and must not be pregnant. A urine pregnancy test will be conducted prior to each session to ensure female subjects do not continue in the study if pregnant. All study subjects will be judged by the medical staff to be psychiatrically and physically healthy and without contraindications/allergies to NAC or ALC.

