1975-2300h	Recreational activities (i.e., movies, magazines, and books).
2300h	Lights out.
0700h	Subject provided a standardized breakfast.
0730-0800h	BAL sample and field sobriety test.
0800h	Discharged from CSC and car keys returned.

Session Activities. On experimental session days, subjects will arrive at the LHBP at the University of Kentucky at 1400h. Upon arrival to the LHBP, the LHBP staff will take the subject's car keys and will return them when the subject is released from the hospital the following morning. Should the subject leave the hospital prior to that time, the LHBP staff or subject will arrange transportation (e.g., arrange a taxi). The car keys will be returned the morning following the experimental session upon successful completion of a field sobriety test.

Behavioral Effects of Drugs: Inpatient (34) (Alcohol and N-Acetylcysteine) (PI: [name].)

Urine and expired breath samples will be obtained for drug and ALC testing. A field sobriety test will be completed. Time of maintenance dosing will be confirmed by self-report and Wisepill® log. If subjects miss more than 3 doses or take doses more than 2 hours outside their scheduled window on 3 occasions within a single dose condition, they will be coached on adherence and that dose condition will be repeated. If this non-adherence occurs again during any other dose condition (or during the repeat condition), the subject will be dropped from the study. Subjects will report their ALC consumption during each 4-day maintenance block using the TLFB (Sobell et al., 1992). Subjects will be then admitted to the CSC at 1500h for their overnight stay and provided a light snack upon admission.

ALC Self-Administration Procedures. The reinforcing effects of ALC, alone and during maintenance on NAC will be assessed using a sophisticated clinical laboratory approach that has predictive validity for AUD pharmacotherapy efficacy (Drobes et al., 2003; Hendershot et al., 2016; O'Malley et al., 2002). The primary outcome measure for this procedure is Number of Drinks Chosen. Testing under this procedure involves two phases: 1) Sampling and 2) Self-Administration.

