Safety and Tolerability Measures. Physiological measures (i.e., BAL measurements, heart rate and blood pressure) will be recorded upon arrival at the LHBP, before ALC administration and throughout the session at the intervals noted in Table 2 using digital monitors. ALC will not be administered if a subject's heart rate is ≥ 100 bpm, systolic pressure is ≥ 150 mmHg or diastolic pressure is ≥ 100 mmHg. A subject will be excluded from further participation if he/she exhibits hypersensitivity (i.e., heart rate > 130 bpm, systolic pressure > 180 mmHg, diastolic pressure > 120 mmHg) during maintenance on NAC and/or to the effects of ALC. The UKU Side Effects Rating Scale will be completed at the end of sessions (Lingjaerde et al., 1987).

Trait Questionnaires and Cognitive Behavioral Tasks. To explore potential mechanisms of NAC effects, subjects will complete a battery of trait measures at screening that assess various aspects of personality, including the Zuckerman-Kuhlman Personality Questionnaire, the Barratt Impulsiveness Scale and the Snaith-Hamilton Pleasure Scale (Patton et al., 1995; Snaith et al., 1995; Zuckerman and Kuhlman, 2000). As outlined in Table 2, subjects will also complete the Commodity Purchase Task, n-back Task, the Go/Stop Task and Money and Alcohol and Money Delay Discounting Tasks. These specific tasks measure several key facets of alcohol-related decision-making and impulsivity (MacKillop, 2016; Reynolds et al., 2008) and, along with the self-administration and subjective effects outcomes described above, model key stages of the addiction cycle (Litten et al., 2016b; MacKillop, 2016).

Commodity Purchase Tasks (Appendix A). Commodity tasks will be used to assess economic demand for alcohol and soda (Amlung et al., 2015; Bruner and Johnson, 2014; Murphy and MacKillop, 2006; Strickland and [name], 2017). In these task subjects are asked to indicate the hypothetical number of items

Behavioral Effects of Drugs: Inpatient (34) (Alcohol and N-Acetylcysteine) (PI: [name].) (e.g., one alcoholic drink) they would purchase at a range of monetary increments (e.g., \$0.00 [free] to \$15/drink). All choices are hypothetical and will not be purchased or administered. Data from the commodity purchase task will be analyzed using economic demand equations previously applied to purchase task data (e.g., Strickland et al., 2016). Primary outcomes of this task include elasticity of demand (α) and intensity of demand (Q_0).

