17. DATA AND SAFETY MONITORING

Data Monitoring Plan. Data will be collected using a computerized data collection and management system. This system automates the collection of the subjective-effect and physiological data, which ensures the accuracy and completeness of data collection. The data are stored in a unique file on the hard drive of the computer and are printed after all the tasks are completed. Paper-and-pencil task data are verified by staff and double-entered into excel spreadsheets after each session. In all instances, the data files do not contain the name of the subject; but instead, a unique four-digit number identifies each subject. A computer file linking the unique number with the subject's name will be kept on a stand-alone, password-protected computer. Data files for experimental tasks and physiological measures from each experimental session will be manipulated and combined into a single electronic spreadsheet for each subject by the PI. Data for all subjects will then be combined into a single electronic spreadsheet and separated by experimental measure for statistical analysis using SPSS (IBM Corporation, Armonk, NY).

The primary outcome for this study will be Number of Drinks during ALC self-administration. Secondary outcome measures will include craving, BALs, physiological and subjective response to ALC, self-reported ALC use in the natural environment during maintenance, as well as performance on cognitive-behavioral tasks, and the Udvalg for Kliniske Undersøgelser (UKU) Side Effects Rating Scale.

As noted above, the majority of data are collected using an automated computer system, which increases the accuracy and completeness of data collection and ensures the validity and integrity of the data. Hand written questionnaires and tasks are double-entered and verified by staff prior to analysis. The initial data manipulation described above will be conducted twice and compared. The quality of manipulated data and data analyses will be monitored by random inspection by the PI and/or Co-Investigators.

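### The primary ANOVA leaves out every subject without all three sessions, so completed data are discarded and the NAC contrast can be biased by an unknown amount

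*Combined protocol and SAP*

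**What the plan says.** Section 4 fixes the accrual target: "We intend to enroll 25 (17 male and 8 female) completers into the study". Sections 7 and 15 repeat that 25 subjects will complete. Section 7 adds that "Completing subjects will experience all dose conditions".

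Section 17 names the endpoint: "The primary outcome for this study will be Number of Drinks during ALC self-administration". Section 7 (Data Analysis) tests it with a "one-factor, repeated-measure ANOVA" in which NAC dose is the only factor. Section 17 names SPSS as the software.

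Subjects can leave after randomisation by four routes:

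- **Positive drug or breath tests on arrival** (Section 7). The first leads to rescheduling; then "Repeated occurrences will result in study dismissal".
- **Non-adherence** (Section 7, Session Activities). The first failure leads to coaching and a repeat of the condition; after a second, "the subject will be dropped from the study".
- **Heart rate or blood pressure limits, on NAC and/or after alcohol** (Section 7, Safety and Tolerability Measures). "A subject will be excluded from further participation if he/she exhibits hypersensitivity".
- **A decision of the responsible medical investigator** (Section 17, Safety Monitoring Plan).

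The documents do not define an analysis population, give a rule for missing sessions, assume a dropout rate, or state how many will be randomised.

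**The concern.** A repeated-measures ANOVA of this kind works on subjects with a value at all three doses. A subject dismissed after one or two sessions contributes nothing, although those sessions were run and measured.

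The second issue is bias. Repeated positive breath tests concern drinking, the cardiovascular rule refers to NAC as well as to alcohol, and Section 9 lists NAC side effects that could affect who stays. Blinding makes the rules the same in each condition. It does not guarantee that they are triggered equally often. If they are triggered more often on NAC among subjects who respond poorly to it, the completers are a favourable selection.

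The result is meant to guide which dose goes forward to a clinical trial. Subjective and safety measures after the sampling dose are to be analysed in the same way, so the same subjects drop out of those comparisons too. Adverse event collection under Section 17 is not affected.

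**Working it through.** **1. The plan's power figure.** Inputs from Section 7: N = 25, f = 0.26, alpha = 0.05, three conditions. Assumed because not stated: correlation 0.5 between sessions and sphericity.

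- Noncentrality = f² × N × m / (1 − rho) = 0.0676 × 25 × 3 / 0.5 = 10.14
- Degrees of freedom 2 and 48; critical F = 3.19; power = 0.795

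This agrees with the stated 0.80. Since 25 is the number of completers, loss does not lower it. For contrast, if only 25 were randomised and 5 were lost, 20 completers would give a noncentrality of 8.11 and power 0.687.

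**2. Sessions discarded.** Reaching 25 completers needs 25 / 0.8 = 31.25, so 32 randomised, at 20% loss, and 25 / 0.6 = 41.7, so 42, at 40% loss. Simulated loss patterns put the unused completed sessions at about 6-9 and 13-23 respectively, against 25 × 3 = 75 analysed. The loss rates are assumptions.

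**3. Precision recovered.** With correlation 0.5 and outcome SD 1, the SE of a dose-placebo contrast from 25 completers is √(2 × 0.5 / 25) = 0.200. A random-intercept model that adds partial subjects, spread evenly over conditions, gives:

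- 3 one-session and 3 two-session subjects: SE 0.192; variance ratio 0.920 (8% lower); effective N 27.2
- 6 and 6: SE 0.185; variance ratio 0.852 (15% lower); effective N 29.3

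Simulations with assumed losses of 15-49% gave variances about 6-18% lower. Other assumed settings ranged from 2% to 22%.

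**4. Bias.** This depends on why and when subjects leave, so several mechanisms were simulated. Rows 1-3 assume SD 2 drinks, correlation 0.5 and 400,000 subjects per setting. Rows 4-5 assume means of 4, 3 and 3 drinks bounded at 0-8, subject and session SDs of 1.6, and an SD of 0 or 1.2 for the individual NAC effect.

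| Reason for loss | Loss | Truth (drinks) | Completers | Mixed model |
|---|---|---|---|---|
| 1. Random, usual drinking, or reactions unrelated to drinking | 20-40% | −1.0 | about −1.0 | – |
| 2. Heavy current drinking, same rule in all conditions | 20%; 40% | −1.0 | −0.95; −0.90 | – |
| 3. Before the session, on NAC only, heavy drinkers | 20%; 40% | 0 | −0.13; −0.27 | −0.17; −0.37 |
| 4. After an observed NAC session with high drinking | 34-43% | −0.87 | −1.23 to −1.41 | −0.93 to −0.95 |
| 5. Before the session, on NAC only (effect SD 0; 1.2) | 38-39% | −0.91; −0.87 | −1.17; −1.33 | −1.26; −1.39 |

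Under the row 4-5 parameters, a rule acting alike after any session left both methods within about 0.1 of the truth (completers −0.86 to −0.94, mixed −0.92 to −0.97, truth −0.87 to −0.91).

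**5. Which timing fits the protocol.** Table 2 puts urine, breath and dosing checks at 1400-1500h and the choice blocks from 1730h. Dismissal for positive tests or non-adherence therefore normally comes before that day's drinking is observed, as in rows 3 and 5. Cardiovascular measures run throughout the session, so that route can act before, during or after the choice blocks.

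**The case against.** A reader might infer that the NAC effect will be badly overstated. The documents do not support that. No rule dismisses anyone for drinking in a session, where up to 8 drinks may be chosen freely. The rules are blinded and identical in every condition, and each completer serves as his or her own control, so loss tied to being a heavy drinker in general cancels from the contrast. A common rule driven by current drinking pulls the estimate toward no effect. Large overstatement appeared only when loss was specific to NAC and linked to poor response, mostly at loss near 40%. The protocol works against such loss: ability to abstain for 12 hours is an entry criterion, a first failure leads to rescheduling or repetition, and adherence and completion are paid for. All of this stands.

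A reader might also infer that a mixed model removes the bias. It does so largely in row 4, where the session that drives dismissal has been observed. In rows 3 and 5 it does slightly worse than the completer analysis, and that timing fits two of the four routes. This objection stands as well.

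Finally, the exclusion of non-completers is inferred from how the ANOVA works, not stated. That is correct, but nothing in the plan offers another way to handle a subject with one or two sessions.

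**Conclusion.** The point holds as a low-cost improvement. As written, the primary analysis leaves out anyone without all three sessions and discards the sessions they completed. The NAC contrast can be biased, but neither direction nor size can be given, because the documents state no dropout rate, SD or correlation; all loss rates and SDs above are assumptions. If dismissal acts alike in all conditions, the bias is small: up to about 0.1 drinks on a true effect near 0.9-1.0.

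Using all sessions lowers the variance of the dose contrast by about 6-18% at assumed losses of 15-49%, and reduces bias when loss follows an observed NAC session. The power statement is not in error on this point.

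**What to change.** In Section 7 (Data Analysis):

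1. State the primary analysis set as all randomised subjects with at least one experimental session.
2. Analyse number of drinks with a linear mixed model (SPSS MIXED, REML), with fixed effects for NAC dose and period and a random subject effect.
3. Keep the completer repeated-measures ANOVA as a sensitivity analysis.
4. Report the number randomised, and tabulate dismissals by reason and by condition at dismissal.
5. State the limitation: the model assumes that loss depends on observed sessions. It does not cure bias when a subject is dismissed before the session in that condition, and it can then be slightly worse than the completer analysis. Items 3 and 4 let the reader judge this.

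The cost is a few sentences and one table, using a standard procedure in the software already named. It needs no extra subjects or visits and no change to the dismissal rules.
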